3.4 Safety Endpoints

Safety and tolerability will be assessed by evaluating DLTs, AEs, physical examinations, and changes in laboratory data (hematology, chemistry, and urinalysis) and vital signs for the entire study treatment duration.

3.5 Pharmacokinetic Endpoints

Values for the pharmacokinetic parameters of venetoclax and ibrutinib will be determined at steady state using noncompartmental methods. The maximum observed plasma concentration (C_{max}), the time to C_{max} (peak time, T_{max}), the area-under-the-plasma concentration-time curve (AUC) over the dosing interval (AUC_{tau}) will be determined. Intensive pharmacokinetic blood samples will be collected.

3.6 Biomarker Research Endpoints

Biospecimens (blood and bone marrow aspirate) will be collected at specified time points ([Appendix E](#)) throughout the study, to evaluate known and/or novel disease-related or drug-related biomarkers. Types of biomarkers may include nucleic acids, proteins, lipids, and/or metabolites, either free or in association with particular cell types. The biomarker research may be exploratory in nature and the results may not be included with the clinical study report. Further details regarding the biomarker research rationale and collection time points are located in the Operations Manual, Section 3.7.

Provision of biospecimens for biomarker research is mandatory, but they will not be collected from sites where local regulations do not allow for the collection, use, and storage of samples as described in the protocol.

4 INVESTIGATIONAL PLAN

4.1 Overall Study Design and Plan

This Phase 2, open-label, single-arm study is designed to evaluate the efficacy and safety of the combination of venetoclax and ibrutinib in Japanese subjects with R/R MCL.

Approximately 12 subjects will receive ibrutinib at 560 mg once daily and venetoclax starting at 20 mg once daily and gradually ramped up to a target dose of 400 mg once daily over a 5 week period.

Dose-limiting toxicities will be evaluated in the first 6 subjects, from Day 1 for a minimum of 5 weeks and at least 1 week of venetoclax dosing at 400 mg, in order to confirm the initial safety and tolerability in Japanese subjects. After the completion of the DLT evaluation period in the first 6 subjects, the AbbVie Study Team and investigators who enrolled the 6 treated subjects will review all available safety and PK data to evaluate the tolerability of venetoclax in combination with ibrutinib in Japanese subjects with R/R MCL. If there are zero or 1 DLTs in the first 6 subjects, enrolment of the additional 6 subjects will proceed. If DLTs are observed in 2 or more of the first 6 subjects, further enrollment in Japan will be interrupted and additional, a detailed safety assessment will be conducted. The Sponsor will consult the Independent Safety Monitor (ISM) with results of the safety evaluation and Sponsor's conclusion on tolerability, then receive the answer from ISM.

To mitigate the risk of TLS, a ramp-up period of approximately 5 weeks will be employed with a stepwise increase of the venetoclax dose ([Figure 1](#)). Subjects will receive a venetoclax dose of 20 mg on Week 1 Day 1 of the ramp-up period and continue with dose increases every 7 days as tolerated. Ramp-up doses of venetoclax include 20 mg, 50 mg, 100 mg, 200 mg, and 400 mg. Subjects will receive ibrutinib at 560 mg once daily starting on Week 1 Day 1.

If one or more electrolyte changes suggestive of TLS occur within 24 hours of the 20 mg dose, no additional venetoclax doses will be administered until resolution. If correction of electrolytes abnormalities is performed, the subsequent dose of venetoclax can only be given when electrolytes have been stable without any more treatment for at least 24 hours. Refer to [Table 2](#), Recommended Dose Modifications for Venetoclax-Related Toxicities, for additional TLS management guidelines. Upon resolution of laboratory abnormalities, the subject will resume at the ramp-up dose. When venetoclax dose interruptions are required during the ramp-up period, the next highest dose level may be initiated 7 days from the start of the current dose level, once the toxicity has resolved to Grade 1 or baseline level and at the investigator's discretion. At the investigator's discretion, the duration of a single dose level during the ramp-up period may be longer than 7 days before increasing to the next highest dose level.

For all ramp-up doses, laboratory values for subject management must be reviewed in real time by the investigator or designee, and prior to the subject's next dose, to ensure appropriate subject management. Based on the laboratory values, the subject may continue dosing, may need to hold dose until resolution, may require hospitalization for further monitoring, or may need additional post-dose laboratory checks.

Initially, subjects at high-risk for TLS will be hospitalized at the start of the venetoclax 20 mg ramp-up dose and again at the start of the 50 mg ramp-up dose for monitoring and prophylaxis of TLS. Subjects will be considered as high-risk for TLS if they have a high tumor burden (at least one lesion > 10 cm; or at least one lesion > 5 cm and circulating lymphocytes > 25,000 cells/mm³) and/or with baseline creatinine clearance (CrCl) < 60 mL/min. Subjects not meeting the high-risk criteria will be considered low risk for TLS. Subjects will be discharged from hospital if there is no evidence of TLS. AbbVie will review the safety data during the course of the study to determine whether continued hospitalization of subjects at high-risk for TLS during ramp-up remains warranted.

Subjects may be treated with venetoclax and ibrutinib for up to 104 weeks, starting with the Week 1 Day 1 venetoclax dose of 20 mg dose during the ramp-up period, followed by ibrutinib monotherapy until disease progression, unacceptable toxicity, or withdrawal of consent. Venetoclax will discontinued

[figure not shown]
after a maximum of 104 weeks of treatment. The study will be discontinued after approval of the venetoclax and ibrutinib combination for R/R MCL in Japan and subjects continuing to derive benefit at that time will transition to commercial supplies.

Subjects who discontinue study treatment for any reason will be followed for progression (if no progression before treatment discontinuation), subsequent anti-cancer therapy, and survival status until study closure.

The schematic of the study is shown in [Figure 1](#). Further details regarding study procedures are included in the Operations Manual.

See [Section 5](#) for information regarding eligibility criteria.

Figure 1. Study Schema

FU = follow-up; MCL = mantle cell lymphoma; PD = disease progression; R/R = relapsed/refractory; wks = weeks

Note: After approval of venetoclax and ibrutinib combination therapy for R/R MCL in Japan, Study M20-075 will be discontinued, and subjects will transition to commercial drug.

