5 STUDY ACTIVITIES

5.1 Eligibility Criteria

Subjects must meet all of the following criteria in order to be included in the study. Anything other than a positive response to the questions below will result in exclusion from study participation.

Consent

- 1. Subjects or their legally authorized representative must voluntarily **sign and date an informed consent** (and assent for minors as required by applicable regulation), approved by an independent ethics committee (IEC)/institutional review board (IRB), prior to the initiation of any screening or study-specific procedures.

Demographic and Laboratory Assessments

- 2. Adult **male or female**, at least 20 years old.
- 3. Adequate hematologic function independent of transfusion and growth factor support for at least 7 days prior to first dose with the exception of pegylated granulocyte-colony stimulating factor (G-CSF; pegfilgrastim) which requires at least 14 days prior to the first dose, defined as:
 - Absolute neutrophil count (ANC) > 1000 cells/mm³ ($1.0 \times 10^9/L$)
 - Platelet count > 50,000 cells/mm³ ($50 \times 10^9/L$)
 - Hemoglobin > 8.0 g/dL.

At the discretion of the investigator: Subjects with bone marrow involvement may be enrolled without meeting the above hematologic function criteria after documented discussion with the AbbVie Therapeutic Area Medical Director (TA MD).

- ✓ 4. Adequate hepatic and renal function defined as:
 - Serum aspartate transaminase (AST) or alanine transaminase (ALT) $\leq 3.0 \times$ upper limit of normal (ULN).
 - Bilirubin $\leq 1.5 \times$ ULN; Subjects with documented Gilbert's syndrome may be allowed with a total bilirubin of $< 5 \times$ ULN.
 - Estimated CrCl ≥ 30 mL/min (Cockcroft-Gault or 24 hour urine collection).
- ✓ 5. Prothrombin time (PT)/international normal ratio (INR) $< 1.5 \times$ ULN and PTT (partial thromboplastin time, activated partial thromboplastin time [aPTT]) $< 1.5 \times$ ULN (unless abnormalities are unrelated to coagulopathy or bleeding disorder). When treated with warfarin or other vitamin K antagonists, then INR ≤ 3.0 .
- ✓ 6. Eastern Cooperative Oncology Group (ECOG) performance status of ≤ 2 .
- ✓ 7. Able to swallow capsules or tablets.
- ✓ 8. Are willing and able to comply with procedures required in this protocol.

Disease Activity

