 - For the purpose of TLS assessment during the DLT evaluation period, only those increases in serum creatinine > 1.0 mg/dL from pre-treatment baseline will be considered clinical TLS.
 - In subjects with renal dysfunction at baseline (CrCl < 60 mL/min), clinical TLS is defined as the presence of laboratory TLS plus either seizures, cardiac dysrhythmia, or death.
- Laboratory TLS: any event that meets Howard criteria ([Appendix G](#)) for laboratory TLS, that does not resolve within 72 hours despite protocol required management.

Major hemorrhage events are defined as:

- Any treatment-emergent Grade \geq 3 hemorrhage AEs (all hemorrhagic events requiring transfusion of red blood cells should be reported as Grade 3 or higher AE per National Cancer Institute (NCI) CTCAE v5.0).
- Any treatment-emergent SAEs of bleeding of any grade
- Any treatment-emergent CNS hemorrhage/hematoma of any grade.

Adverse Event Severity and Relationship to Study Drug

The investigator will rate the severity of each AE according to the NCI CTCAE Version 5.0. If a reported AE increases in severity, the initial event should be given an outcome date and a new AE must be reported to reflect the change in severity. For all reported SAEs that increase in severity, the supplemental eCRFs also need to be updated to reflect any changes due to the increase in severity.

For AEs not captured by the NCI CTCAE, the following criteria should be used:

Grade 1	Mild; asymptomatic or mild symptoms; clinical diagnostic observations only; intervention not indicated.
Grade 2	Moderate; minimal, local or noninvasive intervention indicated; limiting age-appropriate instrumental activities of daily living.
Grade 3	Severe or medically significant but not immediately life-threatening; hospitalization or prolongation of hospitalization indicated; disabling; limiting self-care activities of daily living.
Grade 4	Life-threatening consequences; urgent intervention indicated.
Grade 5	Death related to adverse event.

The investigator will use the following definitions to assess the relationship of the AE to the use of study drug (venetoclax and ibrutinib):

Reasonable Possibility	After consideration of factors including timing of the event, biologic plausibility, clinical judgment, and potential alternative causes, there is sufficient evidence (information) to suggest a causal relationship.

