DLT = dose limiting toxicity; G-CSF = granulocyte-colony stimulating factor; TLS = tumor lysis syndrome

a. Venetoclax dose reduction is not allowed during the DLT assessment period.

Consider discontinuing venetoclax for subjects who require dose reductions to less than 100 mg for more than 2 weeks.

If the dose of venetoclax is reduced, at the investigator's discretion, the dose of venetoclax may be re-escalated after 2 months of a dose reduction in the absence of a recurrence of the toxicity that led to the reduction. Subsequent dose re-escalations should be discussed with the AbbVie TA MD.

Table 3. Dose Modification for Toxicity During Venetoclax Treatment

Dose at Interruption	Restart Dose ^a
400 mg	300 mg
300 mg	200 mg
200 mg	100 mg

a. Continue the reduced dose for at least 1 week before increasing the dose.

Prophylaxis and Management of Tumor Lysis Syndrome

Venetoclax can cause rapid reduction in tumor and thus poses a risk for TLS in the ramp-up period. Changes in electrolytes consistent with TLS that require prompt management can occur as early as 6 to 8 hours following the first dose of venetoclax and at each dose increase. The risk of TLS is a continuum based on multiple factors, including comorbidities. Subjects with high tumor burden are at greater risk of TLS when initiating venetoclax. Reduced renal function further increases the risk. The risk may decrease as tumor burden decreases with continued venetoclax treatment.

Tumor burden assessments, including radiographic evaluation (e.g., CT scan) should be performed at Screening as well as blood chemistry assessments (potassium, phosphorus, calcium, uric acid, creatinine, lactate dehydrogenase, and, if available, albumin, corrected calcium, and ionized calcium) in all subjects. Pre-existing abnormalities should be corrected prior to initiation of treatment with venetoclax.

- High risk for TLS: Subjects with high tumor burden (at least one lesion > 10 cm; or at least one lesion > 5 cm **and** circulating lymphocytes > 25,000 cells/mm³) and/or with baseline CrCl < 60 mL/min.
- Low risk for TLS: Subjects not meeting the criteria described above.

The prophylaxis measures listed below should be followed and more intensive measures (including hospitalization) should be employed for subjects at high-risk for TLS based on local guidelines or institutional standards:

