APPENDIX G. HOWARD CRITERIA FOR LABORATORY AND CLINICAL TUMOR LYSIS SYNDROME

Metabolic Abnormality	Criteria for Classification of Laboratory Tumor Lysis Syndrome ^a	Criteria for Classification of Clinical Tumor Lysis Syndrome ^a
Hyperuricemia	Uric acid > 8.0 mg/dL (475.8 µmol/liter) in adults or above the upper limit of the normal range for age in children	
Hyperphosphatemia	Phosphorus > 4.5 mg/dL (1.5 mmol/liter) in adults or > 6.5 mg/dL (2.1 mmol/liter) in children	
Hyperkalemia	Potassium > 6.0 mmol/liter	Cardiac dysrhythmia or sudden death probably or definitely caused by hyperkalemia
Hypocalcemia	Corrected calcium < 7.0 mg/dL (1.75 mmol/liter) or ionized calcium < 4.5 mg/dL (1.12 mmol/liter) ^b	Cardiac dysrhythmia, sudden death, seizure, neuromuscular irritability (tetany, paresthesia, muscle twitching, carpopedal spasm, Troussseau's sign, Chvostek's sign, laryngospasm, or bronchospasm), hypotension, or heart failure probably or definitely caused by hypocalcemia
Acute kidney injury ^c	Not applicable	Increase in the serum creatinine level of 0.3 mg/dL (26.5 µmol/liter) (or a single value > 1.5 times the upper limit of the age-appropriate normal range if no baseline creatinine measurement is available) or the presence of oliguria, defined as an average urine output of < 0.5 mL/kg/hr for 6 hours

- a. In laboratory TLS, two or more metabolic abnormalities must be present during the same 24 hour period within 3 days before the start of therapy or up to 7 days afterward. Clinical TLS requires the presence of laboratory TLS plus an increased creatinine level, seizures, cardiac dysrhythmia, or death.
- b. The corrected calcium level in milligrams per deciliter = measured calcium level in milligrams per deciliter + 0.8 × (4 - albumin in grams per deciliter).
- c. Acute kidney injury is defined as an increase in the creatinine level of at least 0.3 mg per deciliter (26.5 µmol per liter) or a period of oliguria lasting 6 hours or more. By definition, if acute kidney injury is present, the patient has clinical TLS. Data about acute kidney injury are from Levin A, Warnock DG, Mehta RL, et al. Improving outcomes from acute kidney injury: report of an initiative. Am J Kidney Dis. 2007;50:1-4.

APPENDIX H. RECOMMENDATIONS FOR INITIAL MANAGEMENT OF ELECTROLYTE ABNORMALITIES AND PREVENTION OF TUMOR LYSIS SYNDROME

Section 1: First Dose of Venetoclax or Dose Escalation

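### For subjects with baseline CrCl < 60 mL/min, clinical TLS has no kidney component, so some renal cases meet neither TLS event definition and clinical TLS counts are not comparable across CrCl groups

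*Protocol*

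**What the plan says.** **Risk group.** Protocol 4.1 gives low clearance as a route to high-risk status: "and/or with baseline creatinine clearance (CrCl") below 60 mL/min. Protocol 6.2 repeats it ("and/or with baseline CrCl < 60 mL/min") and comments: "Reduced renal function further increases the risk". Eligibility criterion 4 in Protocol 5.1 admits estimated CrCl from 30 mL/min upward ("Cockcroft-Gault or 24 hour urine collection"), so the affected range is 30 to below 60 mL/min.

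**Event definitions.** Protocol 6.1 takes the Howard criteria in Appendix G as the base for clinical TLS and states two exceptions.

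- During the DLT evaluation period, "only those increases in serum creatinine > 1.0 mg/dL from pre-treatment baseline will be considered clinical TLS".
- In subjects with baseline CrCl below 60 mL/min, "clinical TLS is defined as the presence of laboratory TLS plus either seizures, cardiac dysrhythmia, or death". This exception is not limited to the DLT period.

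Laboratory TLS is an event in 6.1 only if it is still unresolved at 72 hours despite management. SAP 10.3 repeats all of this.

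**Base criteria.** Appendix G includes an increased creatinine among the findings that turn laboratory TLS into clinical TLS. It defines acute kidney injury as a creatinine rise of at least 0.3 mg/dL or six hours of oliguria. Footnote c adds: "By definition, if acute kidney injury is present, the patient has clinical TLS".

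**Other outputs.** SAP 10.3 reports how many subjects meet the Howard laboratory criteria, using uric acid, potassium, phosphorus and calcium over the first 7 days from first dose. SAP Appendix B finds TLS adverse events with a narrow MedDRA query. Neither is restricted by CrCl.

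**The concern.** Low clearance puts a subject in a protocol-designated high-risk group, and the same characteristic removes kidney injury from what counts as clinical TLS in that subject. Pre-existing renal impairment does not by itself explain the removal. Appendix G measures kidney injury as a change, and uses an absolute creatinine limit only when no baseline value exists. Appendix H also acts on creatinine change (25% or more from baseline) without exempting low-clearance subjects. So the plan treats the change as informative for management but not for classification.

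At stake is the final safety report. TLS is one of two adverse events of special interest in Protocol 6.1. If its clinical form is defined differently according to a risk factor for it, the count cannot be read across subjects, and some renal events carry no TLS label under either definition.

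**Working it through.** The plan states no TLS rate or TLS-based calculation, so there is no figure to reproduce. The sample-size calculation (12 subjects, at least 5 complete responses) does not depend on this point. The check is a comparison of definitions.

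**Step 1. One clinical picture, three classifications.** Take a subject with laboratory TLS and a creatinine rise, and no seizure, dysrhythmia or death.

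| Baseline CrCl | Period | Clinical TLS? |
|---|---|---|
| 60 or above | outside DLT period | yes, from a rise of 0.3 mg/dL (Appendix G) |
| 60 or above | DLT period | only if the rise exceeds 1.0 mg/dL (6.1, first exception) |
| 30 to below 60 | any | no, whatever the rise (6.1, second exception) |

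The last row reads the second exception as a complete definition for these subjects. Neither document says which exception takes precedence for such a subject inside the DLT period.

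**Step 2. Do other routes catch the last row?**

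- *Laboratory TLS event (6.1, SAP 10.3):* yes if unresolved at 72 hours; no if it resolves sooner.
- *Howard laboratory count (SAP 10.3):* catches the laboratory abnormality, but creatinine is not among its four analytes. The window is 7 days from first dose. Protocol 4.1 raises the dose every 7 days through five levels, so the window essentially covers the 20 mg level and not the four later ones.
- *MedDRA query (SAP Appendix B):* catches the case if TLS was reported as an adverse event. Under Protocol 6.1 a laboratory abnormality becomes an adverse event only on stated conditions.
- *DLT (Protocol 6.3):* catches a related Grade 3 or higher event, but only among the subjects assessed for DLT. TLS is not named there.
- *CTCAE shift tables and Grade 3 to 4 listings (SAP 10.3):* show chemistry values but do not join laboratory TLS to kidney injury.

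The gap is therefore laboratory TLS that resolves within 72 hours, with kidney injury seen only in creatinine, at CrCl below 60. It meets neither TLS event definition, and no planned output reports laboratory TLS plus kidney injury by baseline CrCl.

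**Step 3. Size.**

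- One case among 12 subjects: 1/12 = 8.3 percentage points.
- The documents give no expected number with CrCl below 60. Assuming 2 to 5 of 12: 2/12 = 17% to 5/12 = 42% of the safety set falls under the narrower definition.
- In the parent study's safety run-in (Protocol 2.1), 15 of 21 subjects (71%) were high-risk by any route. There was one laboratory TLS event, in a high-risk subject, and no clinical TLS. Assuming that 1/15 applies here, 2 to 5 subjects give 2 × 1/15 = 0.13 to 5 × 1/15 = 0.33 expected laboratory TLS cases, before kidney injury is required.

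**The case against.** The strongest reply is that this is an announced exception. Protocol 6.1 starts from Howard, says that it departs from it, and the SAP copies the departure exactly. That stands: the two documents agree, and the modification is not an accident. What is missing is a rationale or a substitute renal criterion.

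It also stands that the two TLS outputs the SAP names outright, the Howard laboratory count and the MedDRA query, do not apply the exception. Only the clinical label is affected.

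Several stronger inferences are tempting, and the documents do not support them.

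- *Renal TLS cannot be counted at all in these subjects.* Step 2 shows several routes that remain open.
- *This is the group most exposed to TLS.* Tumor burden is a parallel route to high-risk status; 6.2 says only that reduced renal function adds to the risk.
- *A high- versus low-risk comparison is distorted.* None is planned; SAP 7.1 lists TLS risk only as a baseline characteristic.
- *Clinical TLS drives the hospitalization review.* Protocol 4.1 refers to safety data and 6.2 to TLS data; neither makes the clinical TLS count the basis.
- *The clinical TLS row of Table 2 is not triggered by kidney injury in these subjects.* Section 6.2 sends the reader to Appendix G for the definition, without the exceptions, so this is not established.
- *The same course would always be clinical TLS just above 60 mL/min.* In the DLT period a doubling from a baseline creatinine of 1.0 mg/dL or less is a rise of at most 1.0 mg/dL, which does not count there either.

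**Conclusion.** The point holds in a limited form. In both documents, on the plain reading of the second exception, no creatinine rise or oliguria can make a case clinical TLS when baseline CrCl is below 60 mL/min, at any time in the study, and no reason is given. Two consequences follow. A subject with quickly resolving laboratory TLS and creatinine-only kidney injury is neither a clinical nor a laboratory TLS event. And clinical TLS counts above and below 60 mL/min measure different things.

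The expected number of affected cases is small: under the run-in assumption, well below one. Each would be worth 8.3 points of a 12-subject rate. The share of subjects with low clearance (17% to 42%) is an assumption only. The efficacy analysis is untouched. The Protocol's summary of changes records that the primary analysis is complete, so the value lies in the final safety report. This is a cheap improvement to reporting and does not show that the reported TLS results are wrong.

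**What to change.** In SAP 10.3, keep the protocol-defined clinical TLS count and state it as an output. Beside it, report the number of subjects with laboratory TLS plus the Appendix G acute kidney injury component, measured from each subject's own baseline and by one rule for everyone. For this row take laboratory TLS by the Appendix G criteria without the 72-hour condition; otherwise it would miss the case it is meant to find. Show both counts by baseline CrCl (below 60, 60 or above).

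In the Protocol, give the reason for the second exception. State which exception governs a subject with CrCl below 60 mL/min in the DLT period. Reconcile 6.1, Table 2, the reference to Appendix G in 6.2, and Appendix G itself, so that it is clear which clinical TLS definition Table 2 uses. Which definition should govern is for the sponsor and investigators to settle.

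The cost is one extra table row from chemistry already collected; oliguria can be included only where urine output was recorded. The downside is that some creatinine rises unrelated to TLS will appear in the added row, so it should be labelled supplementary.
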